8.2.2. Secondary Outcomes

There are a number of secondary outcome measures from the time of randomisation including:

- Recurrent VTE or clinically relevant bleeding at 6 months and 12 months (as assessed through HES records)
- Net clinical benefit composite of clinically relevant bleeding and recurrent VTE at 3 and 6 months.
- New diagnosis of pulmonary hypertension or right ventricular dysfunction within 12 months of SSPE, defined from HES clinical coding and supported where possible by additional radiological data and echocardiograms undertaken in tertiary pulmonary hypertension centres.
- All-cause mortality at 3, 6 and 12 months
- VTE related mortality at 3, 6 and 12 months
- Cardiovascular mortality at 3, 6 and 12 months defined as cardiac deaths (e.g., cardiogenic shock, fatal arrhythmia, cardiac rupture) and vascular deaths (e.g., VTE-related, fatal stroke, ruptured aortic aneurysm, aortic dissection).
- Reclassification rate from thoracic radiologist review

8.2.2.1. Economic

- Healthcare resource use: hospitalisations, bed days, unscheduled primary and secondary care visits for recurrent VTE, clinically relevant bleeding or potentially related symptoms
- Healthcare costs
- Health-related quality of life (EQ-5D-5L at baseline, 3 and 6 months)
- Cost-utility at 6 months (cost per QALY) and cost-effectiveness at 12 months (cost per VTE avoided)

8.2.2.2. Mechanistic (behavioural)

• Themes from qualitative interviews which inform optimal recruitment strategies including information presentation and attitudes to risk.

8.3. Study procedures

The following assessments should be performed at baseline:

- Ethnicity
- Concomitant medications
- Smoking status
- Risk factors for bleeding as defined by ISTH
- VTE symptoms include pleuritic pain, breathlessness, chest pain not pleuritic, syncope, haemoptysis, leg pain (unilateral/bilateral), leg swelling or oedema (unilateral/bilateral)
- VTE recurrence risk factors as defined by ACCP
- Height and weight
- Routine blood tests to include Hb, platelet count, creatinine, eGFR, BNP, NT-proBNP, Troponin T, D dimer
- Modified MRC dyspnoea score
- EQ-5D-5L questionnaire to be completed on paper by patient (only required for patients who will be randomised)

At point of randomisation:

• Provide patient with patient card

The following assessments should be performed at 4 week follow up via telephone call with the patient (a window of one week is permitted) and review of the medical record:

- SAE check
- Survival check
- VTE recurrence
- Anti-coagulation medication check to include cessation of treatment, commencement of treatment and change to type of treatment

The following assessments should be performed at 12 week and 24 week follow up via telephone call with the patient (a window of two weeks is permitted) and review of the medical record:

- SAE check
- Survival check
- VTE recurrence
- Bleeding events major bleeding and clinically relevant non major bleeding
- Anti-coagulation medication check to include cessation of treatment, commencement of treatment and change to type of treatment
- Modified MRC dyspnoea score
- EQ-5D-5L questionnaire
- NHS usage for VTE recurrence and associated symptoms/bleeding events- to include primary care visits, emergency department/ambulatory care/AMU visits, hospitalisations and diagnostic investigations for VTE.

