2. AIMS AND OBJECTIVES

2.1. Pilot Stage Objectives

The internal pilot will be conducted during the first 12 months of recruitment and has the following objectives:

- 1. To assess recruitment rates, the nature of exclusions and patients who decline.
- 2. To assess acceptability of the study to patients and clinicians and early identification of recruitment barriers.
- 3. To assess safety with respect to SSPE diagnosis (see 3.1.1 Nested CTPA Study).
- 4. To refine recruitment target based on misclassification rates.

Table 1: RAG rating for internal pilot

Table 1: 10 to facing for internal prior			
	% of patients declining no treatment	Patients recruited per site	
Red	≥70%	< 0.5 per month	
Amber	30-69%	0.5 – 1.5 per month	
Green	<30%	≥1.5 per month	

We have taken guidance from a Medical Research Council Hubs for Trials Methodology Research workshop into account when determining stop/go criteria and will report our pilot results according to their suggestions (27). Areas considered by the workshop as suitable progression criteria included recruitment rate, protocol adherence and outcome rate. As described in Table 1, the traffic light system of green (go), amber (amend) and red (stop) was deemed preferable to a simple stop/go approach when specifying progression criteria for internal pilot studies, and they suggested recruitment progression criteria should be based on rates per centre per unit time that can be extrapolated, rather than specifying an absolute number by a specific date.

Our first major progression criterion is the proportion of otherwise eligible patients excluded due to declining no treatment (green=<30%, amber= 30-69%, red= \geq 70%). Our second criterion is recruitment rate. If sites, overall, recruit 1.5 patients per month on average, and each site has a target of 30 patients each site will complete recruitment in 20 months; this represents green as recruitment would complete by 32 months, assuming a linear rate of site opening. If overall recruitment was 1 patient/site/month we would approach more sites to open, and if there were <0.5 patients/site/month this represents red (stop). We will collect safety data about VTE outcomes at 4 weeks after randomisation. The DMC will review safety data with respect to SSPE diagnosis (see 3.1.1 Nested CTPA Study) and recurrent VTE and recommend whether the trial should progress or not.

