8.2.1. Multiple (joint) Primary Outcomes

Composite of recurrent VTE (nonfatal) and/or VTE related death (primary safety outcome) and clinically relevant bleeding, which is a composite of major and clinically relevant non-major bleeding (CRNMB) (primary efficacy outcome) within 3 months post-randomisation.

The following primary outcome definitions will be used by the CIAC:

VTE recurrence

Composite of nonfatal VTE (PE or DVT) recurrence and/or VTE-related death.

PE recurrence

Suspected (new or recurrent) PE with one of the following findings:

- A new intraluminal filling defect in a subsegmental or more proximal pulmonary artery on CTPA or CT thorax with IV contrast
- An extension of an existing subsegmental pulmonary embolism on CTPA or CT thorax with IV contrast
- A new perfusion defect of at least 75% of a segment with a local normal ventilation result (high-probability) on ventilation/perfusion lung scan

 Symptoms suggestive of PE but with an inconclusive CTPA, CT thorax with IV contrast or ventilation/perfusion scan for PE, and with evidence of a new DVT in the lower extremities by compression ultrasound or venography.

DVT recurrence

Suspected (recurrent) DVT with one of the following findings:

- abnormal compression ultrasound
- an intraluminal filling defect on venography (CT/MR/invasive)

Objective testing for PE/DVT recurrence will be encouraged, but in the absence of objective testing, a suspected episode of DVT or PE will be considered as confirmed if it led to a change in anticoagulant treatment at therapeutic dosages.

VTE-related death

- PE based on objective diagnostic testing, autopsy, or
- Death which cannot be attributed to a documented cause and for which PE/DVT cannot be ruled out (unexplained death).

Clinically relevant bleeding

Composite of major bleeding and clinically relevant non major bleeding (CRNMB).

Major bleeding

Is defined by ISTH criteria:

- 1. Fatal bleeding, and/or
- 2. Symptomatic bleeding in a critical area or organ, such as intracranial, intraspinal, intraocular, retroperitoneal, intra-articular or pericardial, or intramuscular with compartment syndrome, and/or
- 3. Bleeding causing a fall in haemoglobin level of 20g L⁻¹ (1.24 mmol L⁻¹) or more, or leading to transfusion of two or more units of whole blood or red cells.

Clinically relevant non-major bleeding (CRNMB)

Is defined by ISTH criteria:

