8.4. Schedule of Assessments

	Screening	Baseline	Telephone Call 1	Telephone Call 2	Telephone Call 3	HES data extraction
			4 weeks (± 1 week)	12 weeks (± 2 weeks)	24 weeks (± 2 weeks)	52 weeks
Consent	X	X				
Eligibility check	Χ	X				
Registration	Χ					
Randomisation		X				
CTPA/CT thorax with contract	Χ					
Medical history	Χ					
Concomitant medications		X				
Ethnicity		X				
Risk factors for bleeding		X				
VTE symptoms and recurrence risk factors		X				
Routine blood tests		Х				
Modified MRC Dyspnoea score		X		X	X	
Pregnancy test	Χ					
Physical exam	Χ					
Vital signs	Χ					
CTPA/CT Thorax upload to PACS		X				
Leg venous ultrasound	Χ					
EQ-5D-5L		X		X	X	
Anticoagulant medication check			X	X	X	
VTE Recurrence			X	X	X	Χ
Bleeding events (major bleeding and clinically relevant non major bleeding)				X	X	Χ
NHS usage for VTE related events/bleeding events				Х	Х	X
SAE check			Х	Х	Х	
Survival check			Х	Х	Х	Х

Notes

- Medical history to include smoking status
- Randomisation provide patient card to patient at point of randomisation
- Bleeding risk factors as defined by ISTH
- Recurrent VTE risk factors as defined by ACCP
- VTE symptoms to include pleuritic pain, breathlessness, chest pain not pleuritic, syncope, haemoptysis, leg pain (unilateral/bilateral), leg swelling or oedema (unilateral/bilateral)
- Routine bloods results to include Hb, platelet count, creatinine, eGFR, BNP, NT-proBNP, Troponin I, Troponin T, D dimer
- Physical examination to include height, weight, pain on lower-limb venous palpation, leg swelling swelling/oedema (unilateral/bilateral), leg erythema (unilateral/bilateral)
- Vital signs to include heart rate, blood pressure, oxygen saturation, respiratory rate
- CTPA/CT thorax upload to PACS to be done immediately following registration of the patient
- Venous ultrasound of both proximal legs using compression ultrasonography from the saphenofemoral junction to the popliteal fossa sampling at three points. If CT/MR venography has already been performed including both proximal legs ultrasonography is not required.
- EQ-5D-5L only required for patients who will be randomised. To be completed on paper by patient at baseline and follow up via telephone call.
- Bleeding events
- Anti-coagulation medication check to include cessation of treatment, commencement of treatment and change to type of treatment

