9.5. Reporting period

Details of targeted AEs as described in section 9.3 will be detected from patient-reported symptoms or clinical records during follow up at 12 and 24 weeks post randomisation and via NHS digital records at 52 weeks post randomisation. Collection of these AEs will help indicate whether the trial intervention is associated with increased adverse events. The reporting timeframe for adverse events is from the date of randomisation until 6 months post randomisation.

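### The 4-week call asks about recurrent VTE but not bleeding, so non-serious bleeds in the first 3 months rest on one structured contact at up to 14 weeks

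*Protocol*

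**What the plan says.** Section 8.2.1 makes recurrent VTE and bleeding joint primary outcomes. The second is "clinically relevant bleeding, which is a composite of major and clinically relevant non-major bleeding (CRNMB) (primary efficacy outcome) within 3 months post-randomisation".

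Section 8.3 sets the contacts:

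- **4 weeks.** "The following assessments should be performed at 4 week follow up via telephone call with the patient (a window of one week is permitted") and a review of the medical record. The items are SAE check, survival check, VTE recurrence and anticoagulant check.
- **12 and 24 weeks.** Also by telephone ("a window of two weeks is permitted) and review of the medical record"). These lists add "Bleeding events major bleeding and clinically relevant non major bleeding" and a question on NHS use for VTE and bleeding that includes primary care visits.

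The schedule in section 8.4 agrees. The row "VTE Recurrence" is marked at 4, 12, 24 and 52 weeks. The row "Bleeding events (major bleeding and clinically relevant non major bleeding") is marked at 12, 24 and 52 weeks only.

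Section 2.1, on the pilot, says "We will collect safety data about VTE outcomes at 4 weeks after randomisation", and has the DMC advise on progression from the SSPE diagnosis data and recurrent VTE. Section 9.5 has targeted adverse events detected "during follow up at 12 and 24 weeks post randomisation", with NHS Digital records at 52 weeks.

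**The concern.** Inside the 3-month primary window, one joint primary outcome is asked about twice and the other once. The bleeding composite includes non-major bleeds that qualify through a single face-to-face evaluation (section 8.2.1). Such a bleed need not be an SAE, and it may have been seen by a GP or another hospital. If it happened in the first weeks, the first direct question about it comes around week 12.

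Three things are at stake:

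- **Completeness.** Missed bleeds shrink the contrast that the superiority test relies on. Blinded adjudication cannot recover an event that was never collated.
- **Balance between arms.** Allocation is open label, so a participant's readiness to recall and mention a minor bleed weeks later could differ by arm. The protocol gives no basis for its direction or size.
- **Early safety view.** For participants between weeks 4 and 12, the data described for the pilot DMC review show the possible harm of withholding treatment (VTE), but not non-serious bleeding on treatment.

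**Working it through.** **1. Timing, from the windows in 8.3 and 8.4**

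- As written, the first bleeding question comes at the latest at 12 + 2 = 14 weeks after randomisation.
- With an item on the 4-week call (week 3 to week 5), the first interval is at most 5 weeks. The next is at most 14 − 3 = 11 weeks, nominally 12 − 4 = 8.

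**2. The protocol's own sample sizes (section 13.1)**

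Bleeding: 7% v 3%, two-sided alpha 0.05, 90% power, mean proportion 0.05:

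n per arm = [1.960·√(2·0.05·0.95) + 1.282·√(0.07·0.93 + 0.03·0.97)]² / 0.04² = 621.8, so 622 per arm and 1244 in total. This matches the protocol.

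VTE: 2% in both arms, margin 2.5%, one-sided alpha 0.025, 90% power:

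n per arm = (1.960 + 1.282)²·2·0.02·0.98 / 0.025² = 659.03, so 660 per arm and 1320 in total. This also matches.

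The evaluable number planned is therefore 660 per arm.

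**3. Power for bleeding if some bleeds are missed**

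Let s be the share of all 3-month bleeds that is missed, the same in both arms. The observed risks are p₁ = 0.07(1−s) and p₂ = 0.03(1−s), with mean p̄, and

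power = Φ{ [p₁ − p₂ − 1.960·√(2p̄(1−p̄)/660)] / √[(p₁(1−p₁) + p₂(1−p₂))/660] }.

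| s (assumed) | Observed risks | Expected events per arm | Power |
|---|---|---|---|
| 0 | 7.0% v 3.0% | 46.2 v 19.8 | 91.6% |
| 6% | 6.58% v 2.82% | 43.4 v 18.6 | 89.8% |
| 10% | 6.3% v 2.7% | 41.6 v 17.8 | 88.5% |
| 20% | 5.6% v 2.4% | 37.0 v 15.8 | 84.4% |

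For s = 0 the bracket is 0.04 − 1.960·0.011997 = 0.016486. Dividing by 0.011947 gives 1.380, and Φ(1.380) = 0.916.

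**4. Which row is relevant**

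The protocol gives no missed share and no timing of bleeds. A 4-week item can recover only bleeds that are early, non-serious, unrecorded and forgotten by week 12. If bleeds were spread evenly over 13 weeks and 20% of those in the first 4 weeks were lost, s = (4/13)·0.20 = 6.2%, close to the 6% row. Front-loaded bleeding would raise this.

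**5. If the loss differs by arm (assumed)**

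- 10% missed only under anticoagulation: 6.3% v 3.0%, power 81.3%.
- 10% missed only without anticoagulation: 7.0% v 2.7%, so the observed difference grows from 4.0 to 4.3 percentage points.

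Nothing in the protocol says which direction, if either, to expect.

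**The case against.** The strongest reply is that the 12-week contact is more than a question from memory. It pairs the bleeding item with a review of the medical record and an NHS-use item that names primary care visits. Section 3.1 also draws on site notes, electronic records and HES. Every non-major bleed in the composite involves a health-care contact, so there will usually be a record somewhere. Bleeds that lead to hospitalisation are SAEs, sought at week 4 and reportable within 24 hours (sections 8.3 and 9.4). The 4-week call is described as a safety call, and sections 2.1, 8.3 and 8.4 are consistent with one another.

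Most of this stands, and it rules out three stronger readings that a reader might infer:

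- **That non-major bleeds rest on recall alone.** Record review and the NHS-use item contradict this.
- **That the DMC will have no bleeding data.** Section 13.3 expects interim analyses, at least annual, that are likely to include the primary outcomes, and serious bleeds are reported as SAEs. Only non-serious bleeding is absent, and only from the 4-week data and the pilot review as described.
- **That section 9.5 favours VTE over bleeding.** It omits week 4 for all targeted events, and section 9.3 lists VTE among them.

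The reply does not close the gap entirely. HES extraction is scheduled at 52 weeks (8.4), while the primary analysis stops at the 12-week assessment (13.4), so on that schedule HES cannot fill it. Site notes may not hold a visit made elsewhere. The NHS-use item is also absent at week 4. A participant who declines further data collection before week 12 (8.5) will have been asked about VTE but not about bleeding.

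**Conclusion.** The point holds as a gap in ascertainment. Bleeding is missing from the 4-week call in both the text and the schedule. Non-serious bleeds in the primary window depend on one structured contact at up to 14 weeks, and the 4-week safety data are one-sided to the same extent.

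The effect on power is probably small: 91.6% falls to 89.8% if 6% of bleeds are missed, or to 88.5% if 10% are. This assumes 660 evaluable per arm, the planned risks of 7% and 3%, and an equal loss in both arms. The 20% row (84.4%) should not be read as the cost of this omission. It would mean losing a fifth of all 3-month bleeds, major ones included, which the protocol does not suggest. A loss that differed by arm would matter more, but its existence and direction are conjecture.

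Both stated sample sizes reproduce and the required number does not change. This is a cheap improvement to make, not an error to correct.

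**What to change.** - **8.3:** add major and clinically relevant non-major bleeding, with date of onset, to the 4-week list.
- **8.4:** mark the bleeding row in the 4-week column.
- **9.5:** add the 4-week time point for targeted adverse events, VTE and bleeding alike.
- **2.1:** state that 4-week bleeding will go to the DMC by arm, beside the 4-week VTE data.

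The cost is one extra CRF item on an existing call and a minor amendment. Participants already past week 4 when it takes effect will lack the item, so early and late recruits will differ in how bleeding was sought. The sample size is unaffected. The interval before the 12-week call shortens to at most 11 weeks; it does not disappear.

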8.4. Schedule of Assessments

	Screening	Baseline	Telephone Call 1	Telephone Call 2	Telephone Call 3	HES data extraction
			4 weeks (± 1 week)	12 weeks (± 2 weeks)	24 weeks (± 2 weeks)	52 weeks
Consent	X	X				
Eligibility check	Χ	X				
Registration	Χ					
Randomisation		X				
CTPA/CT thorax with contract	Χ					
Medical history	Χ					
Concomitant medications		X				
Ethnicity		X				
Risk factors for bleeding		X				
VTE symptoms and recurrence risk factors		X				
Routine blood tests		Х				
Modified MRC Dyspnoea score		X		X	X	
Pregnancy test	Χ					
Physical exam	Χ					
Vital signs	Χ					
CTPA/CT Thorax upload to PACS		X				
Leg venous ultrasound	Χ					
EQ-5D-5L		X		X	X	
Anticoagulant medication check			X	X	X	
VTE Recurrence			X	X	X	Χ
Bleeding events (major bleeding and clinically relevant non major bleeding)				X	X	Χ
NHS usage for VTE related events/bleeding events				Х	Х	X
SAE check			Х	Х	Х	
Survival check			Х	Х	Х	Х

Notes

- Medical history to include smoking status
- Randomisation provide patient card to patient at point of randomisation
- Bleeding risk factors as defined by ISTH
- Recurrent VTE risk factors as defined by ACCP
- VTE symptoms to include pleuritic pain, breathlessness, chest pain not pleuritic, syncope, haemoptysis, leg pain (unilateral/bilateral), leg swelling or oedema (unilateral/bilateral)
- Routine bloods results to include Hb, platelet count, creatinine, eGFR, BNP, NT-proBNP, Troponin I, Troponin T, D dimer
- Physical examination to include height, weight, pain on lower-limb venous palpation, leg swelling swelling/oedema (unilateral/bilateral), leg erythema (unilateral/bilateral)
- Vital signs to include heart rate, blood pressure, oxygen saturation, respiratory rate
- CTPA/CT thorax upload to PACS to be done immediately following registration of the patient
- Venous ultrasound of both proximal legs using compression ultrasonography from the saphenofemoral junction to the popliteal fossa sampling at three points. If CT/MR venography has already been performed including both proximal legs ultrasonography is not required.
- EQ-5D-5L only required for patients who will be randomised. To be completed on paper by patient at baseline and follow up via telephone call.
- Bleeding events
- Anti-coagulation medication check to include cessation of treatment, commencement of treatment and change to type of treatment
- NHS usage for VTE recurrence and associated symptoms/bleeding events to include primary care visits, emergency department/ambulatory care/AMU visits, hospitalisations and diagnostic investigations for VTE

8.5. Participant Withdrawal and Changes of Status Within Trial

Informed consent is defined as the process of learning the key facts about a clinical trial before deciding whether or not to participate. It is a continuous and dynamic process and participants should be asked about their ongoing willingness to continue participation. Participants should be aware at the beginning that they can freely withdraw (discontinue participation) from the trial at any time. A participant who withdraws from the trial does so completely (i.e. from trial treatment and all follow up).

A participant who wishes to cease to participate *in a particular aspect of the trial*, will be considered as having changed their status within the trial.

Patients who lose mental capacity during the trial will be withdrawn as they would not be able to comply with taking the medication or form completion.

The changes in status within the trial are categorised in the following ways:

- No trial intervention: The participant would no longer like to receive the trial intervention, but is willing to be followed up in accordance with the schedule of assessments and if applicable using any central UK NHS bodies for long-term outcomes (i.e. the participant has agreed that data can be collected and used in the trial analysis).
- No trial related follow-up: The participant would no longer like to receive the trial
 intervention AND does not wish to attend trial visits in accordance with the schedule
 of assessments but is willing to be followed up at standard clinic visits and if
 applicable using any central UK NHS bodies for long-term outcomes (i.e. the
 participant has agreed that data can be collected at standard clinic visits and used in
 the trial analysis, including data collected as part of long-term outcomes).
- No further data collection: The participant would no longer like to receive the trial intervention AND is not willing to be followed up in any way for the purposes of the trial AND does not wish for any further data to be collected (i.e. only data collected prior to the withdrawal can be used in the trial analysis).

The details of either withdrawal or change of status within trial (date, reason and category of status change) should be provided via trial exit/change of status form within the CRF and clearly documented in the source documents. Patients subsequently found to be ineligible will still have their data analysed.

If following central thoracic radiologist review of the participants' CTPA or CT Thorax, it is found that a randomised participant has a PE affecting a larger vessel or no SSPE is present, providing their continuing consent they should continue to be followed up as part of the trial. All patients will be analysed for the primary outcome, and as per protocol analysis will be undertaken on patients with a confirmed diagnosis of ISSPE.

